TFLs	tables, figures, and listings
TND	target not detected
WBC	white blood cell
WHO	World Health Organization

1. INTRODUCTION

This statistical analysis plan (SAP) describes the statistical analysis methods and data presentations to be used in the tables, figures, and listings (TFLs) in the clinical study report (CSR) for Study GS-US-337-1746. The SAP is based on the study protocol amendment 2 dated 23 July 2015 and the electronic case report form (eCRF). However, the study was early terminated after 87 subjects were enrolled due to lack of feasibility of enrolling originally planned 430 subjects. Statistical analysis methods also changed corresponding to the sample size change. Detailed changes are documented in Section 6.4.

Any changes made after the finalization of the SAP will be documented in the CSR.

1.1. Study Objectives

[figure not shown]
The primary objectives of this study are as follows:

- To evaluate the efficacy of treatment with ledipasvir/sofosbuvir fixed-dose combination (LDV/SOF FDC) for 12 or 24 weeks, with or without ribavirin (RBV), as measured by the proportion of subjects with sustained virologic response 12 weeks after discontinuation of therapy (SVR12)
- To evaluate the safety and tolerability of LDV/SOF FDC with or without RBV for 12 or 24 weeks, as assessed by review of the accumulated safety data

The secondary objectives of this study are as follows:

- To determine the proportion of subjects who attain SVR at 4 and 24 weeks after discontinuation of therapy (SVR4 and SVR24)
- To determine the proportion of subjects with virologic failure
- To evaluate the emergence of viral resistance to SOF and LDV during treatment and after treatment discontinuation among subjects with virologic failure

The exploratory objectives of this study are as follows:

1.2. Study Design

This is a Phase 3b, multicenter, open label study in adult male and female subjects with chronic genotype (GT) 1 or 4 hepatitis C virus (HCV) infection and who have failed prior SOF-based HCV therapy, including in combination with simeprevir (SMV) \pm RBV or with RBV \pm pegylated interferon (PEG).

Approximately 50% of subjects enrolled may have had prior treatment with SOF + SMV \pm RBV. Approximately 5% of subjects may be infected with GT 4 HCV.

Approximately 430 subjects are planned to enroll into 2 cohorts:

- **Cohort 1:** subjects without cirrhosis (n=180) will be randomized in a 1:1 ratio into Group 1 and 2:

Group 1: LDV/SOF FDC tablet (LDV 90 mg/SOF 400 mg) once daily for 12 weeks

Group 2: LDV/SOF FDC tablet (LDV 90 mg/SOF 400 mg) once daily and RBV at a total daily oral dose of 1000-1200 mg divided twice a day (BID) for 12 weeks

- **Cohort 2:** subjects with compensated cirrhosis (n=250) will be randomized in a 1:1 ratio into Groups 3 and 4:

Group 3: LDV/SOF FDC tablet (LDV 90 mg/SOF 400 mg) once daily and RBV at a total daily oral dose of 1000-1200 mg divided BID for 12 weeks.

Group 4: LDV/SOF FDC tablet (LDV 90 mg/SOF 400 mg) once daily for 24 weeks

Randomization will be stratified by genotype 1 or 4, and by prior SOF therapy in combination with SMV or without SMV

The schedule of assessments is provided as an appendix to the SAP ([Appendix 2](#)).

The total time to complete all study visits is up to approximately 42 or 54 weeks (group 4 only) including the following periods:

- Up to 42-day (6-week) screening period
- A 12-week treatment period for Groups 1 - 3, and 24-week treatment period for Group 4
- Up to 24-week posttreatment period

The study was early terminated after 87 subjects were enrolled due to lack of feasibility of enrolling originally planned 430 subjects.

1.3. Sample Size and Power

Cohort 1: For the non-inferiority comparison of SVR12 in the noncirrhotic cohort (group 1 vs. 2) with a 10% non-inferiority margin, a sample size of 90 subjects per treatment group will provide at least 90% power to establish non-inferiority at 1-sided 0.025 level, assuming the SVR12 rates are 98% for both groups.

Cohort 2: For the non-inferiority comparison of SVR12 in the compensated cirrhotic cohort (group 3 vs. 4) with a 10% non-inferiority margin, a sample size of 125 subjects per treatment group will provide at least 90% power to establish non-inferiority at 1-sided 0.025 level, assuming the SVR12 rates are 95% for both groups.

However, the study was early terminated after 87 subjects were enrolled due to lack of feasibility of enrolling originally planned 430 subjects.

2. TYPE OF PLANNED ANALYSIS

2.1. Data Monitoring Committee

This study does not have a data monitoring committee.

2.2. Interim Analysis

2.2.1. Posttreatment Week 12 Analysis

The analysis for the primary endpoint SVR12 will be conducted after all subjects complete the Posttreatment Week 12 visit or prematurely discontinue from study. All the safety and efficacy data through the Posttreatment Week 12 visit will be cleaned, finalized and included for the analysis.

2.3. Final Analysis

After all subjects have completed the study, outstanding data queries have been resolved, and the database has been cleaned and finalized, the final analysis of the data will be performed.

3. GENERAL CONSIDERATIONS FOR DATA ANALYSES

Analysis results will be presented using descriptive statistics. For categorical variables, the number and percentage of subjects in each category will be presented; for continuous variables, the number of subjects [n], mean, standard deviation [SD] or standard error [SE], median, first quartile [Q1], third quartile [Q3], minimum, and maximum will be presented.

Data collected in the study will be presented in by-subject listings for all subjects in the Safety Analysis Set, unless otherwise specified. All by-subject listings will be presented by subject identification (ID) number in ascending order, unless otherwise specified.

Analyses on efficacy will be presented by each treatment group and total for each cohort and overall, while on other analyses, like safety analyses, demographics and baseline characteristics will be presented by each treatment group for each cohort and overall.

3.1. Analysis Sets

Analysis sets define the subjects to be included in an analysis. Analysis sets and their definitions are provided in this section. The number of subjects eligible for each analysis set will be provided. Subjects who were excluded from each analysis set will be summarized or provided in a by-subject listing with reasons for exclusion by treatment group.

3.1.1. All Randomized/Enrolled Analysis Set

The All Randomized/Enrolled Analysis Set includes all subjects who were randomized or enrolled in the study. Subjects are grouped within the All Randomized/Enrolled Analysis Set according to the treatment they actually received.

3.1.2. Full Analysis Set

The Full Analysis Set (FAS) includes all enrolled subjects who took at least 1 dose of study drug. The study drugs in this study are LDV/SOF FDC, with or without RBV. The difference between the FAS definition provided in the protocol and this SAP is documented in Section [6.4](#).

3.1.2.1. Full Analysis Set by Randomized Treatment

Subjects are grouped according to the treatment they were randomized. This is the primary analysis set for efficacy analyses.

3.1.2.2. Full Analysis Set by Actual Treatment

Subjects are grouped according to their cirrhotic status and the treatment/duration they actually received. This is applied for key efficacy analyses.

3.1.3. Safety Analysis Set

The Safety Analysis Set includes all subjects who took at least 1 dose of study drug. Subjects are grouped according to the treatment they actually received.

This is the primary analysis set for safety analyses.

3.2. Subject Grouping

For analyses based on the All Randomized/Enrolled Analysis Set or FAS by Randomized Treatment, subjects will be grouped according to the treatment to which they were randomized. For analyses based on other analysis sets, such as the Safety Analysis Set and FAS by actual treatment, subjects will be grouped according to the actual treatment received. The actual treatment received is defined as the randomized treatment except for subjects who received treatment that differs from the randomized treatment for the entire treatment duration. In this case, the actual treatment received is defined as the treatment received for the entire treatment duration.

Randomized Treatment groups will be:

1. Cohort 1 subjects received LDV/SOF 12 week
2. Cohort 1 subjects received LDV/SOF + RBV 12 weeks
3. Cohort 2 subjects received LDV/SOF + RBV 12 week
4. Cohort 2 subjects received LDV/SOF 24 weeks

Due to randomization errors, cirrhotic subjects might be included in cohort 1 and non-cirrhotic subjects might be included in cohort 2 for some efficacy analyses by randomized treatment group.

Actual Treatment groups will be:

1. Cohort 1 Non-cirrhotic subjects received LDV/SOF 12 week
2. Cohort 1 Non-cirrhotic subjects received LDV/SOF + RBV 12 weeks
3. Cohort 2 Cirrhotic subjects received LDV/SOF + RBV 12 week
4. Cohort 2 Cirrhotic subjects received LDV/SOF 24 weeks

3.3. Strata and Covariates

Approximately 430 subjects will be enrolled into 2 cohorts. In each cohort, subjects will be randomized at a 1:1 ratio into two treatment groups (Non-cirrhotic subjects for cohort 1 and Cirrhotic subjects for cohort 2) via the interactive web response system (IWRS) using a stratified randomization schedule.

Stratification will be based on the following variables:

- HCV genotype 1 or 4
- Prior SOF therapy in combination with SMV or without SMV

If there are discrepancies in stratification factor values between the IWRS and the clinical database, the values recorded in the clinical database will be used for analyses and a listing is provided to document those discrepancies.

3.4. Examination of Subject Subsets

Subsetting of subjects based on randomization stratification factors will be explored for subgroup analyses. If there are discrepancies in stratification factor values between the IWRS and the clinical database, the values recorded in the clinical database will be used for analyses.

The subject subsets will be explored for the primary efficacy endpoint, SVR12 and Virologic Outcomes using both FAS populations. The presumed prognostic baseline characteristics include the following:

- age (< 65 years, \geq 65 years)
- sex (male, female)
- race (white, black, other)
- ethnicity (Hispanic or Latino, not Hispanic or Latino)
- baseline BMI (< 30 kg/m², \geq 30 kg/m²)
- baseline RAVs (yes, no, not-determined)
- baseline albumin (<=3.5 g/dL, >3.5 g/dL)
- baseline platelets (<=75,000/ μ L, 75,000 - <=100,000/ μ L, >100,000/ μ L)
- HCV subgenotype (1, 4; with 1 further broken down to 1a, 1b, No confirmed subtype)
- cirrhosis (presence, absence, missing if any)

- IL28B (CC, non-CC; with non-CC further broken down to CT, TT)
- baseline HCV RNA (< 800,000 IU/mL, \geq 800,000 IU/mL)
- prior HCV treatment experience (treatment naive, treatment experienced)
- the most recent HCV treatment combinations (SOF + SMV, SOF + SMV + RBV, SOF + RBV, SOF + PEG + RBV)
- number of prior HCV treatment regimens (1, 2, or 3 or more)
- completed study treatment, discontinued study treatment
- adherence to study regimen (< 80%, \geq 80%)
- adherence to LDV/SOF (< 80%, \geq 80%)
- adherence to RBV (Group 2 and 3 only) (< 80%, \geq 80%)

3.5. Multiple Comparisons

No multiplicity adjustment will be made for testing since the statistical comparisons performed are for exploratory purpose only between group 1 vs group 2, and between group 3 vs group 4 due to small sample size actually enrolled.

3.6. Missing Data and Outliers

In general, missing data will not be imputed unless methods for handling missing data are specified.

3.6.1. Missing Data

For missing last dosing date of study drug, imputation rules are described in Section 3.8.1. The handling of missing or incomplete dates for adverse event (AE) onset is described in Section 7.1.5.2, and for prior and concomitant medications in Section 7.4.

For analyses of categorical HCV RNA data, missing posttreatment HCV RNA data will have the missing data imputed. Missing on-treatment HCV RNA will have missing data imputed up to the time of the last dose (for on-treatment displays). If the study day associated with the last dosing date of any study drug is greater than or equal to the lower bound of a visit window, and the value at the visit is missing, then the value will be imputed. If the study day associated with the last dosing date is less than the lower bound of a visit window then the on-treatment value at that visit will remain missing.

If an HCV RNA data point is missing and is preceded and followed in time by values that are “< LLOQ target not detected (TND),” then the missing data point will be set to “< LLOQ TND.”

If a data point is missing and preceded and followed by values that are “< LLOQ detected,” or preceded by “< LLOQ detected” and followed by “< LLOQ TND,” or preceded by “< LLOQ TND” and followed by “< LLOQ detected,” then the missing value will be set to “< LLOQ detected.” In these situations the data point will be termed a bracketed success; otherwise, the data point will be termed a bracketed failure (ie, \geq LLOQ detected). If a data point is missing and is not bracketed, the missing data point will also be termed a failure (ie, \geq LLOQ detected) except for SVR24, which will be imputed according to SVR12 status. Success for SVR12 who have no further HCV RNA measurements collected will be counted as a success for SVR24 due to the high correlation between these 2 endpoints.

For the analyses of continuous HCV RNA efficacy data, when a missing HCV RNA value is imputed as < LLOQ TND or < LLOQ detected according to the imputation rule described above, the corresponding continuous value will be imputed to LLOQ – 1 IU/mL. No other imputation will be performed for continuous HCV RNA data.

For health-related quality of life data including SF-36, CLDQ-HCV, FACIT-F, and WPAI:Hep C, missing data at on-treatment visits, posttreatment follow-up Week 4 (FU-4) visit, and posttreatment follow-up Week 12 (FU-12) visit will not be imputed. Last posttreatment observation carried forward will be used for imputation of missing data at posttreatment follow-up Week 24 visit.

3.6.2. Missing Date

For missing last dosing date of study drug, imputation rules are described in Section 3.8.1. The handling of missing or incomplete dates for adverse event (AE) onset is described in Section 7.1.5.2, and for prior and concomitant medications in Section 7.4.

For some countries, only birth year is collected on the eCRF. In those cases, “01 January” will be used for the unknown birth day and month for the purpose of age calculation, unless age is captured on the CRF.

3.6.3. Outliers

Outliers will be identified during data management and data analysis process, but no sensitivity analyses will be conducted. All data will be included in the data analysis.

3.7. Data Handling Conventions and Transformations

By-subject listings will be presented for all subjects in the Safety Analysis Set sorted by subject ID number, visit date, and time (if applicable) unless otherwise specified. Data collected on log forms, such as AEs, will be presented in chronological order within subject.

Age (in years) on the date of the first dose of study drug and sex at birth will be used for analyses and presentation in listings.

If a subject was not dosed with study drug at all, then the date the informed consent was signed will be used instead of the first dose date of study drug.

Non-PK data that are continuous in nature but are less than the lower limit of quantitation or above the upper limit of quantitation will be imputed as follows:

- A value that is one unit less than the limit of quantitation will be used for calculation of descriptive statistics if the datum is reported in the form of “ $< x$ ” (where x is considered the limit of quantitation). For example, if the values are reported as < 50 and < 5.0 , values of 49 and 4.9, respectively, will be used for calculation of summary statistics. An exception for this rule is any value reported < 1 . For the values reported as < 1 or < 0.1 , value of 0.9 or 0.09 will be used for calculation of summary statistics.
- A value that is one unit above the limit of quantitation will be used for calculation of descriptive statistics if the datum is reported in the form of “ $> x$ ” (where x is considered the limit of quantitation). Values with decimal points will follow the same logic as above.
- The limit of quantitation will be used for calculation of descriptive statistics if the datum is reported in the form of “ $\leq x$ ” or “ $\geq x$ ” (where x is considered the limit of quantitation).

The COBAS® AmpliPrep/COBAS® TaqMan® HCV Quantitative Test, version 2.0 was used to determine HCV RNA results in this study. The lower limit of quantitation (LLOQ) of the assay is 15 IU/mL.

When the calculated HCV RNA IU/mL is within the linear range of the assay, then the result will be report as the “<< numeric value>> IU/mL.” This result will be referred to in this document as the numeric result or as “ \geq LLOQ detected” for categorical result.

When HCV RNA is not detected, the result is reported as “No HCV RNA detected” or “target not detected”. This result will be referred to in this document as “ $<$ LLOQ target not detected” or “ $<$ LLOQ TND.”

When the HCV RNA IU/mL is less than LLOQ of the assay, the result is reported as “ < 15 IU/mL HCV RNA detected.” This result will be referred to in this document as “ $<$ LLOQ detected.”

The overall category of HCV RNA $<$ LLOQ includes “ $<$ LLOQ TND” and “ $<$ LLOQ detected.”

For numerical HCV RNA data, values below LLOQ will be set to the LLOQ – 1 IU/mL (ie, 14 HCV RNA IU/mL). HCV RNA values returned as “target not detected” will also be set to LLOQ – 1 IU/mL.

If methods based on the assumption that the data are normally distributed are not adequate, analyses may be performed on transformed data (eg, log10 scale) or nonparametric analysis methods may be used, as appropriate.

3.8. Visit Windows

3.8.1. Definition of Study Day

Study day is the day relative to the date of the first dose of study drug. Study Day 1 will be defined as the day of first dose of study drug administration.

Study day will be calculated from the date of first dose of study drug administration and derived as follows:

- For postdose study days: Assessment Date – First Dose Date + 1
- For days prior to the first dose: Assessment Date – First Dose Date

The last dose date for an individual study drug will be the end date on study drug administration eCRF for the record where the “subject permanently discontinued” flag is ‘Yes’. The last dose date will be defined as the maximum of the last dose dates of individual study drugs in a treatment group.

If there are subjects for whom the date of last study drug is unknown due to the reason that the subject was lost to follow-up and not able to be contacted, the date of last dose will be estimated using the maximum of nonmissing study drug start or stop dates, visit dates, and laboratory collection dates (posttreatment visits and unscheduled visits are not included).

3.8.2. Analysis Windows

Subject visits might not occur on protocol-specified days. Therefore, for the purpose of analysis, observations will be assigned to analysis windows.

In general, the baseline value will be the last nonmissing value on or prior to the first dose date of study drug.

HCV RNA, vital signs, and safety laboratory data collected up to the last dose date + 3 days are considered to be on-treatment data and HCV RNA, vital signs, and safety laboratory data collected after the last dose date + 3 days are considered posttreatment data. The analysis windows for on-treatment HCV RNA, vital signs and safety laboratory data are provided in [Table 3-1](#).

Table 3-1. Analysis Windows for On-treatment HCV RNA, Vital Signs and Safety Laboratory Data

Nominal Visit	Cohort 1: Subjects Without Cirrhosis					
	Group 1 (LDV/SOF 12 Weeks)			Group 2 (LDV/SOF+RBV 12 Weeks)		
	Nominal Day	Lower Limit	Upper Limit	Nominal Day	Lower Limit	Upper Limit
Baseline	1	(none)	1	1	(none)	1
Week 1	7	2	11	7	2	11
Week 2	14	12	21	14	12	21
Week 4	28	22	42	28	22	42
Week 8	56	43	70	56	43	70
Week 12	84	71	≥ 85	84	71	≥ 85

Nominal Visit	Cohort 2: Subjects With Cirrhosis					
	Group 3 (LDV/SOF+RBV 12 Weeks)			Group 4 (LDV/SOF 24 Weeks)		
	Nominal Day	Lower Limit	Upper Limit	Nominal Day	Lower Limit	Upper Limit
Baseline	1	(none)	1	1	(none)	1
Week 1	7	2	11	7	2	11
Week 2	14	12	21	14	12	21
Week 4	28	22	42	28	22	42
Week 8	56	43	70	56	43	70
Week 12	84	71	≥ 85	84	71	98
Week 16	NA			112	99	126
Week 20	NA			140	127	154
Week 24	NA			168	155	≥ 168

HCV RNA, vital sign, and safety laboratory data collected after the last dose date + 3 days will be assigned to the posttreatment follow-up (FU) visit. Visit windows will be calculated from the last dose date (ie, FU Day = collection date minus the last dose date) as shown in [Table 3-2](#).

Table 3-2. Analysis Windows for Posttreatment HCV RNA, Vital Signs and Safety Laboratory Data

Nominal FU^a Visit	HCV RNA			Vital Signs and Safety Laboratory Data^b		
	Nominal FU Day	Lower Limit	Upper Limit	Nominal FU Day	Lower Limit	Upper Limit
FU-4	28	21	69	28	4	30
FU-12	84	70	146	84	31	146
FU-24	168	147	210	168	147	210

a FU-x visit = posttreatment Week-x follow-up visit.

b Vital signs and safety labs will only be summarized for the FU-4 visit (up to 30 days after last dose), the time windows after FU-4 was for listing purpose only.

3.8.3. Selection of Data in the Event of Multiple Records in an Analysis Window

Depending on the statistical analysis method, single values may be required for each analysis window. For example, change from baseline by visit usually requires a single value, whereas a time-to-event analysis would not require 1 value per analysis window.

If multiple valid nonmissing numeric observations exist in an analysis window, records will be chosen based on the following rules if a single value is needed:

- For baseline, the last available record on or prior to the date of the first dose of study drug will be selected. If there are multiple records with the same time or no time recorded on the same day, average (arithmetic mean) will be used for the baseline value. If multiple electrocardiogram (ECG) measurements occur on the same day prior to first dose of any study drug, the average will be used as baseline for continuous data, regardless of the timing of these multiple ECG measurements.
- For postbaseline visits:
 - The record closest to the nominal day for that visit will be selected except for HCV RNA posttreatment follow-up visits, for which the latest record in the analysis window will be selected.
 - If there are 2 records that are equidistant from the nominal day, the later record will be selected.
 - If there is more than 1 record on the selected day, the average will be taken, unless otherwise specified.

If multiple valid nonmissing categorical observations exist in a window, records will be selected as follows:

- For baseline, the last available record on or prior to the date of the first dose of study drug will be selected. If there are multiple records with the same time or no time recorded on the same day, the value with the lowest severity will be selected (eg, normal will be selected over abnormal). If multiple ECG measurements occur on the same day prior to first dose of any study drug, the value with the lowest severity will be selected regardless of the timing of these multiple ECG measurements.
- For postbaseline visits, follow the same rules described above for postbaseline numeric observations, except that if there are multiple records on the same day, the most conservative value will be selected (eg, abnormal will be selected over normal).

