4.2.1. Duration of Exposure to Study Drug

Total duration of exposure to study drug will be defined as last dose date minus first dose date plus 1, regardless of any temporary interruptions in study drug administration, and will be expressed in weeks using up to 1 decimal place (eg, 4.5 weeks).

The total duration of exposure to study drug will be summarized using descriptive statistics (n, mean, SD, median, Q1, Q3, minimum, and maximum) and using the number of subjects (ie, cumulative counts) and percentage of subjects exposed through the following time periods: baseline (Day 1), Week 1 (Day 7), Week 2 (Day 14), Week 4 (Day 28), Week 10 (Day 70), Week 12 (Day 84), and Week 16 (Day 112), Week 20 (Day 140), and Week 24 (Day 168), with Week 16 to Week 24 for group 4 only. A 3-day window is applied to the last planned on-treatment visit to match with the protocol-specified visit window, ie, Groups 1 -3 subjects will have number of subjects exposed through week 12 calculated as the number of subjects who were exposed study drug for at least 81 days. Similarly, Group 4 subjects will have number of subjects exposed through week 24 calculated as the number of subjects who were exposed study drug for at least 165 days. Summaries will be provided by treatment group for each cohort and overall for the Safety Analysis Set.

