Appendix 2. Schedule of Assessments

	Screen	Baseline/ Day 1 ^a	On-Treatment Study Week (± 3 Days)								Posttreatment Study Week (± 5 Days)		
			1	2	4	8	12	16 ^b	20 ^b	24 ^b	ET	4 ^c	12 ^c
Clinical Assessments													
Informed Consent		X											
Determine Eligibility	X	X											
Medical History	X												
Historical Resistance Test Data ^d	X												
Physical Examination	X	X					X ^e			X ^e	X		
Height	X												
Weight	X	X											
Vital Signs	X	X	X	X	X	X	X	X	X	X	X	X	X
12-Lead ECG	X												
Imaging for HCC ^f	X												
Adverse Events	X	X	X	X	X	X	X	X	X	X	X	X	
Concomitant Medications	X	X	X	X	X	X	X	X	X	X	X	X	
Pregnancy Prevention Counseling		X	X	X	X	X	X	X	X	X	X	X	X
Health Related Quality of Life Surveys		X			X		X			X	X	X	X
Study Drug Dispensing		X ^g			X	X	X ^h	X ^h	X ^h				
Review of Study Medication Adherence (Pill Count)			X	X	X	X	X	X	X	X	X		

				On-Treatment Study Week (± 3 Days)								Posttreatment Study Week (± 5 Days)			
		Screen	Baseline/ Day 1 ^a	1	2	4	8	12	16 ^b	20 ^b	24 ^b	ET	4 ^c	12 ^c	24
Laboratory Assessments															
Hematology, Chemistry	X	X	X	X	X	X	X	X	X	X	X	X	X		
Coagulation Tests	X	X					X			X	X				
HCV RNA	X	X	X	X	X	X	X	X	X	X	X	X	X	X	
Viral Sequencing/phenotyping ⁱ		X	X	X	X	X	X	X	X	X	X	X	X	X	
Pregnancy Testing ^j	X	X			X	X	X	X	X	X	X	X ^k	X ^k	X ^k	
Urinalysis & Urine Drug Screen	X														
HCV Genotyping, IL28B	X														
HCV, HIV, HBV Serology	X														
TSH, HbA1c, Fibrotest [®] /APRI	X														
Future Research Blood Sample ^l		X					X			X	X				

a Baseline/Day 1 assessments must be performed prior to dosing

b On-Treatment Visits at Weeks 16, 20 and 24 are only applicable to subjects in study group 4

c All subjects will complete the posttreatment Week 4 and Week 12 visits ; subjects with HCV RNA < LLOQ at the posttreatment (PT) Week 12 visit will complete the PT Week 24 visit

d Collect and record information regarding historical resistance test data if available

e A physical exam will be performed at the end of treatment visit (Week 12 for study groups 1,2,3; and Week 24 for study group 4)

f Liver imaging within 6 months prior to Baseline/Day 1 is required in subjects with cirrhosis to exclude HCC

g The IWRS will provide randomization to study Group

h Study drug dispensing at Week 12, 16 and 20 is only applicable to study group 4

i Plasma samples will be collected and stored for potential HCV sequencing/phenotyping and other virology studies.

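### Table 3-1 assigns Study Day 11 to Week 1, although on the SAP's own nominal days and ±3-day visit window it is a Week 2 day; only Week 2 descriptive displays can be affected

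*SAP*

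**What the plan says.** Table 3-1 in Section 3.8.2 lists the on-treatment windows for HCV RNA, vital signs and safety laboratory data. For each group it gives nominal day, lower limit and upper limit, and the first three post-baseline rows are the same in all four groups:

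- "Week 1 7 2 11 7 2 11"
- "Week 2 14 12 21 14 12 21"
- "Week 4 28 22 42 28 22 42"

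Four other places bear on how these limits work.

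- Section 3.8.1 numbers the first dose as Day 1: "For postdose study days: Assessment Date – First Dose Date + 1".
- Section 4.2.1 maps weeks to days in the same way as the table, "Week 1 (Day 7), Week 2 (Day 14), Week 4 (Day 28", and counts its 3-day allowance from Days 84 and 168 (at least 81 and 165 days of exposure): "A 3-day window is applied to the last planned on-treatment visit to match with the protocol-specified visit window".
- Appendix 2 sets the permitted visit window in the column header "On-Treatment Study Week (± 3 Days".
- Section 3.8.3 decides between several post-baseline records in one window: "The record closest to the nominal day for that visit will be selected". The later record is taken if two are equidistant. Post-treatment HCV RNA follows a different rule that is not relevant here.

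**The concern.** An analysis window should contain every day on which its visit may take place. The Week 2 window does not. A subject who attends Week 2 three days early, as the schedule allows, has the results filed under Week 1. They then compete with the real Week 1 results and normally lose.

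Week 2 is then empty for that subject although a sample was taken on schedule. Hemoglobin, platelets and vital signs lose a Week 2 value and its change from baseline. Continuous HCV RNA at Week 2 is excluded unless it is bracketed by values < LLOQ (Section 6.2.2). Categorical HCV RNA at Week 2 is imputed under Section 3.6.1, provided the last dose falls on or after the lower bound of the window. If the Week 1 visit was missed, the Week 2 sample is labelled Week 1.

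**Working it through.** **Step 1. The cut-points in Table 3-1 against the midpoints of adjacent nominal days.** Midpoint = (earlier nominal day + later nominal day) / 2.

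| Nominal days | Midpoint | Printed upper limit of earlier visit |
|---|---|---|
| 7, 14 | 10.5 | 11 |
| 14, 28 | 21 | 21 |
| 28, 56 | 42 | 42 |
| 56, 84 | 70 | 70 |
| 84, 112 (Group 4) | 98 | 98 |
| 112, 140 (Group 4) | 126 | 126 |
| 140, 168 (Group 4) | 154 | 154 |

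Six of the seven cut-points equal the midpoint. The first does not: |11 − 7| = 4 and |11 − 14| = 3, so Day 11 is given to the farther visit.

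**Step 2. Permitted visit days (Appendix 2, ±3 days, on the printed nominal days).** Week 1: 7 − 3 = 4 to 7 + 3 = 10. Week 2: 14 − 3 = 11 to 14 + 3 = 17. Day 11 is permitted for Week 2 and not for Week 1. The same check on Weeks 4, 8, 12, 16, 20 and 24 finds no permitted day outside its own window. Day 11 is the only one in the table.

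**Step 3. Selection under Section 3.8.3 when the Week 2 visit is on Day 11.**

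- Week 1 visit on Days 4 to 10: its distance from Day 7 is at most 3, against 4 for Day 11. The Week 1 record is chosen, Day 11 is dropped and Week 2 is empty.
- Week 1 visit on Day 3: both records are 4 days away, so the later one, Day 11, is reported as Week 1.
- Week 1 visit on Day 2, or missed: Day 11 is reported as Week 1.

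In the last two cases Week 2 is again empty.

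**Step 4. What Section 3.6.1 then does with categorical HCV RNA.** Take a subject ≥ LLOQ at Week 1, < LLOQ on Day 11 and < LLOQ at Week 4.

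- If bracketing uses the selected visit values, the neighbours of Week 2 are Week 1 (≥ LLOQ) and Week 4 (< LLOQ). Week 2 becomes a bracketed failure and is shown as ≥ LLOQ.
- If bracketing uses all observed records, the neighbours are Day 11 and Week 4, both < LLOQ. Week 2 is shown as < LLOQ, and the continuous value is set to LLOQ − 1, as the observed one would have been.

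Section 3.6.1 speaks of values that precede and follow in time and does not say which of the two is meant.

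**Step 5. Possible number of subjects.** The SAP gives no visit dates, so this is assumption only. Suppose every Week 2 visit falls on Days 11 to 17, with weights exp(−(day − 14)² / (2 SD²)).

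- SD 1.5: 0.1353 / 3.694 = 3.7%; × 82 = 3.0 subjects.
- SD 2: 0.3247 / 4.627 = 7.0%; × 82 = 5.8 subjects.
- Uniform: 1/7 = 14.3%; × 82 = 11.7 subjects.

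The 82 treated subjects are 15, 17, 26 and 24 by randomized group (Section 6.4.2). One subject is therefore between 1/26 = 3.8% and 1/15 = 6.7% of a group.

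**The case against.** The SAP states no rule for setting window limits. The midpoint pattern is inferred, and 7 and 14 are the only adjacent pair whose midpoint is not a whole number. Some rounding was needed, and 11 is 10.5 rounded up. This explains how 11 may have arisen. It does not remove the conflict with the permitted visit days.

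The strongest argument is that sites might count Week 1 as seven days after Day 1, which is Day 8, and Week 2 as Day 15. The ±3-day ranges would then be Days 5-11 and 12-18, which match the printed boundary exactly, and no Day 11 visit would be an on-schedule Week 2 visit. Appendix 2 gives no day numbers. Against this stand the nominal days 7 and 14 printed in Table 3-1, and Section 4.2.1, which uses the same days and counts the 3-day allowance from Days 84 and 168. Section 4.2.1 concerns exposure, but it says that the allowance is there to match the protocol's visit window. On the Day 8/15 basis the next midpoints would be (15 + 29)/2 = 22 and (29 + 57)/2 = 43, and the table has 21 and 42. The SAP as written therefore supports Days 7 and 14. What stands is that the number of affected visits may be zero.

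A reader might also infer that observed HCV RNA results are discarded and that responders will be shown as ≥ LLOQ at Week 2. The SAP does not support this without qualification. The record leaves only the single-value by-visit analyses and stays in the data and listings. The false ≥ LLOQ result depends on the first reading in Step 4. Misclassification in SVR12 by early viral response is possible but not shown, because Section 6.1.3 does not define the categories or say whether Week 2 is used.

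**Conclusion.** The Week 1/Week 2 boundary in Table 3-1 is inconsistent with the table's own nominal days and with the ±3-day window in Appendix 2. A Week 2 visit on Day 11 is always filed under Week 1 and leaves Week 2 empty.

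The reach is narrow. The displays that can change are Week 2 HCV RNA < LLOQ by visit, continuous HCV RNA, hemoglobin, platelets and vital signs, and possibly SVR12 by early viral response. When a Day 11 record is taken as Week 1, the Week 1 entry of the same by-visit displays carries the Week 2 sample. Other laboratory analytes are summarized only at end of treatment and posttreatment Week 4 (Section 7.2.1). SVR12, the non-inferiority comparisons, virologic failure, worst-grade laboratory summaries and listings do not depend on this boundary.

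The number of subjects is unknown. It may be zero. The figure of about 3 to 12 of 82 rests wholly on the assumed spreads in Step 5, and its upper end needs as many visits three days early as on the target day. Severity is minor.

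**What to change.** In Table 3-1, for all four groups, set Week 1 to Days 2-10 and Week 2 to Days 11-21. All permitted Week 1 days (4-10) and Week 2 days (11-17) then fall in their own windows, and no other cut-point changes.

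The cost is two limits per group in one table and the matching change in the windowing program. No new data are needed. If the SAP is already final, Section 1 provides for recording the change in the clinical study report.
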